Iron and erythropoietin are linked by each playing a role in the oxygen sensing pathway regulated by hypoxia inducible factor (HIF). We know that HIF plays a key role in sensing low oxygen, and thus plays a key role regulating human's response to low oxygen during acute and chronic exposure to high altitude. By using these compounds to modulate the HIF pathway we propose to discover the most important components of the pathway for overcoming hypoxia exposure in healthy, fit humans.

B. Specific Aims/Study Objectives

The overarching goal of the study is to determine the effect of iron and erythropoietin (EPO) supplementation on acute and chronic physiological responses to high altitude.

[figure not shown]
Specific aims

1. To determine the effects of iron and EPO on exercise performance acutely (first 3 days), during acclimatization (days 7-8), and chronically (days 13-14) at altitudes of 10,000 to 14,000 feet in PFO- and PFO+ subjects.
2. To determine the effects of iron and EPO on acute and chronic changes in hemoglobin (Hb) mass, cognitive performance, ventilation, and molecular markers of hypoxia exposure at altitudes of 10,000 to 14,000 feet in PFO- and PFO+ subjects.
3. To determine the effects of iron and EPO on development of acute mountain sickness (AMS) at altitudes of 10,000 to 14,000 feet in PFO- and PFO+ subjects.

Please note that all baseline studies will provide novel data on men and women with and without a patent foramen ovale (PFO) so that even if the altitude studies become unfeasible, new information will be gained from these studies.

C. Methods, Materials and Analysis

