5. Code Substitution—Simultaneous, a measure of visual scanning and attention, learning, and immediate recall of digit-symbol pairings;
6. Code Substitution—Delayed Recall, a measure of short-term memory for digit-symbol pairings;
7. Spatial Discrimination, a measure of visuospatial analytic ability;
8. Matching to Sample, an assessment of attention and memory for visuospatial discrimination;
9. Sternberg's Memory Search, a measure of working memory for letters.

The total time required to complete the battery of tests is ~20 minutes. DANA will be administered once at sea level (baseline day 3) and in the evening of days 1, 3, 7, and 13 at high altitude.

Acute Mountain Sickness (AMS) and oxygen saturation (SpO₂): The severity of AMS symptoms will be determined using a subset of the Environmental Symptoms Questionnaire (ESQ) and the Lake Louise AMS Questionnaire (LLQ), the two most common and accepted measures of AMS.

The ESQ is a self-reported, 68-question inventory used to document symptoms induced by high altitude and other stressful environments. A weighted average of scores from 9 symptoms (headache, lightheaded, dizzy, etc.) designated AMS-C will be calculated. AMS-C scores greater than 0.7 are considered positive for AMS (77).

The LLQ consists of a six question self-reported assessment of AMS symptoms, with a score of ≥ 3 , including headache, defined as AMS. The high altitude-illness assessment questionnaires will be administered on paper forms and tabulated in digital format at the end of each day (78).

After completing the AMS assessment forms, arterial saturation will be monitored by pulse oximetry. Each AMS assessment and pulse oximetry measurement will take ~10 minutes to complete. These measurements will be made once at baseline, immediately upon arrival at high altitude, and every night and morning of days 1, 2, 3, 7, and 13 at high altitude. Based on our previous study of 164 subjects, this ascent profile induced symptoms of AMS in ~50% of the subjects on the first evening at high altitude.

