5k run: The 5-kilometer run will be performed as part of the APFTs at baseline (see above) and on its own on days 1, 7 and 13 in Colorado. The run will be performed on a 400 m track or local running trail (Pre's trail) in Eugene, OR and on the high school track or local paved trails near the research site in Colorado. Subjects will be asked to complete the run as fast as possible while being timed.

Drug intervention: In a single-blind, randomized, placebo-controlled design, subjects will receive a placebo (saline placebo), iron, or erythropoietin.

Iron. Volunteers will receive an intravenous injection of Fe(III)-hydroxide sucrose (200 mg) or placebo twice before high altitude exposure, once 4 weeks and once within several days before traveling to high altitude. All subjects will report to the lab as if they are receiving iron, but only those randomly assigned to the iron arm will receive iron. The remaining subjects will receive intravenous saline. This is infused over the course of approximately 2-5 minutes. This is the same dose shown to prevent AMS, and to block hypoxia-induced pulmonary hypertension²⁸. All subjects, regardless of whether they receive iron or placebo, will remain in the lab for an additional 15 minutes after administration to ensure they do not have an allergic reaction (see risks below) and to ensure placebo subjects are blinded to the treatment.

EPO. Volunteers will receive a sub-cutaneous injection of epoetin alpha 150 IU/kg injections given weekly (50 IU/kg 3 x week) for three consecutive weeks prior to high altitude exposure. This dose and timing match the AMS prevention study protocol of Heo et al.¹¹

To ensure subjects are blinded to the intervention, all subjects will have the same intervention schedule. For those in the iron group, they will come to the lab 3x per week as required by the EPO intervention schedule, for example, and receive saline interventions. For those in the EPO group, they will come to the lab one time 4 weeks prior to departing to Colorado to receive a placebo injection while the iron group receives their iron injection. The placebo group will receive saline at all visits.

The table below provides the intervention schedule for each group. Blue indicates the placebo group, red indicates the iron group, and green indicates the EPO group.

	Sunday	Monday	Tuesday	Wednesday	Thursday	Friday	Saturday
4 weeks until departure				Saline Iron Saline			

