3 weeks until departure		Saline Saline EPO		Saline Saline EPO		Saline Saline EPO	
2 weeks until departure		Saline Saline EPO		Saline Saline EPO		Saline Saline EPO	
1 week until departure		Saline Saline EPO		Saline Iron EPO		Saline Saline EPO	Departure

Rucksack carry: Subjects will be instructed to complete a 3.1-mile uphill hike as fast as possible while carrying a 35-pound backpack. We previously developed this test to simulate military style field operations for another DoD funded study. The course follows a rugged hiking/jeep trail that begins in a wooded area at ~10,500 feet and ends on a ridge above tree line at ~12,500 feet. Subjects will hike the course as a group after the 5k run first day at high altitude to familiarize themselves with the terrain. The following morning (2nd day) they will be asked to complete the course as fast as possible while being timed. Subjects will also run the course on days 8 and 14. Fit subjects, free of AMS, can finish the course in ~60 minutes.

Traveling and accommodations:

Subjects will be transported to Denver, Colorado in groups of 10-20 by commercial airlines or bus and then immediately driven to Leadville or Breckenridge, Colorado by charter buses. The total travel time from baseline to high altitude will be ~8 hours. Subjects will follow a strict regimen of tasks designed to simulate a high level of physical activity at high altitude (10,000 to 14,000 feet) over three days and two nights (acute) followed by 11 additional days of residence at high altitude (chronic exposure) before returning to Oregon on the 14th day.

Subjects will be housed and fed in condominiums in the Leadville or Breckenridge area. All meals will be cooked and served communally. Omnivorous and vegetarian options will be provided. Subjects will sleep in individual beds, but will share quarters and bathrooms (see note below about COVID management in 'COVID-19 exposure scenario'). Caffeine intake will be limited to the equivalent of two cups of coffee per day. Subjects will refrain from taking any non-study related supplements (over-the-counter, prescription, and recreational) or other non-study drugs or alcohol for the duration of the study beginning with baseline studies through the completion of the study. Violation of these policies will yield a subject's data invalid for the whole study, and thus will result in expulsion from the study and prorated payment.

D. Research Population & Recruitment Methods

Participant population

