All expenses (airfare, lodging and food) will be paid for the subject's trip to Colorado. Subjects will receive a check for a total of \$1000, if they complete the entire study. Subjects will be mailed a check for \$600 by Research Logistics LLC, the study sponsor, approximately 2 weeks after completion of the study and they will receive a separate check for \$400 from the University of Oregon's Cardiopulmonary and Respiratory Physiology Laboratory. If subjects do not complete all study procedures or violate the study rules (such as drinking alcohol or excess caffeine or violating CDC guidelines for lessening COVID-19 exposure risks), payment will be prorated based on the above compensation schedule, e.g., if subjects complete baseline screening and performance stabilization before dropping out they will be paid \$100. Subjects who do not comply with the study rules will be housed until they are able to be sent home on the next available flight without excessive costs to the investigators and will be paid only for the portions of the study they have completed before they were removed from the study.

E. Informed Consent Process

Informed consent will be administered to each subject by the PI and colleagues. The PI is well versed in the process of informed consent and has trained his co-investigators thoroughly on how to best perform this procedure. The PI will ensure that all investigators obtaining consent have experience in the informed consent procedure and are capable of adequately discussing the related physiology, study procedure and potential risks.

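### A rule breach after randomisation voids all of a subject's data, and no analysis set keeps that subject in the comparison

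*Combined protocol and SAP*

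**What the plan says.** The rule is in section C, under Traveling and accommodations. The paragraph first sets a caffeine limit: "Caffeine intake will be limited to the equivalent of two cups of coffee per day". It then bans other substances: "Subjects will refrain from taking any non-study related supplements (over-the-counter, prescription, and recreational) or other non-study drugs or alcohol", from the baseline studies to the end of the study. The consequence follows: "Violation of these policies will yield a subject's data invalid for the whole study, and thus will result in expulsion from the study", with prorated payment.

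Other sections bear on how this rule would work:

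- **Drug intervention (section C):** "In a single-blind, randomized, placebo-controlled design, subjects will receive a placebo (saline placebo), iron, or erythropoietin". Only subjects are described as blinded.
- **Specific Aims (section B):** Aim 3 is the effect of iron and EPO on AMS. The same section says the baseline studies yield new PFO information even if the altitude part proves unfeasible.
- **AMS and oxygen saturation (section C):** in the team's previous study, "this ascent profile induced symptoms of AMS in ~50% of the subjects on the first evening at high altitude".
- **Altitude associated risks (section G):** AMS symptoms will not be treated and should be gone by day 3.
- **Compensation (section D):** excess caffeine and alcohol are both named as rule violations. The stated consequences are removal and prorated payment; data are not mentioned.

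The title promises a statistical analysis plan. The text has no intention-to-treat, full or per-protocol set, and no method for missing data.

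**The concern.** One sentence joins a conduct rule (expulsion) to a data rule (everything void). Followed as written, it removes randomised subjects for what they did after assignment, so the groups compared need no longer be the groups that were randomised.

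The link to AMS is plausible. A subject with an untreated headache who takes a remedy becomes a violator because of the outcome. If voiding follows AMS, AMS incidence is understated and a true difference shrinks. If voiding also differs by arm, a false difference can appear. It could differ by arm through a drug effect on AMS, or because whoever rules on a breach knows the arm; no passage says who that is.

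Data already collected are also lost. A breach during the dosing weeks erases the baseline data. A breach late in the Colorado stay also erases the day 1 5k run and the first-evening AMS scores. A similar bias in the performance outcomes is possible but is not quantified here.

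**Working it through.** The plan states no alpha, power, effect size, dropout or violation rate, so there is no figure to reproduce. What follows is an illustration, and every voiding rate in it is assumed.

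**Inputs**

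- Per arm, assuming equal allocation: 80/3 ≈ 27 (Day 5, Performance Stabilization) or 100/3 ≈ 33 (Participant population; the 80 plus 20 alternates also make 100).
- Placebo AMS, p: 50% from the AMS section. The alternative of 30% is an assumption, made because Altitude associated risks expects AMS in fewer people than the up to 40% who feel lightheaded, dizzy or breathless.
- Drug AMS: assumed at 0.4 times placebo, so 20% or 12%.
- e: the share of AMS cases voided.

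**Formula.** Observed AMS = p(1 − e)/(1 − pe).

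Example with e = 0.10:

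- Placebo: 0.50 × 0.90/(1 − 0.05) = 0.45/0.95 = 0.474
- Drug: 0.20 × 0.90/(1 − 0.02) = 0.18/0.98 = 0.184
- Difference: 29.0 points instead of 30

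Power and type I error come from exact enumeration of the two-sided pooled z-test at 0.05, averaged over the binomial number voided in each arm.

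**Same e in both arms, true drug effect**

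| e | 50% v 20%: difference | Power, 27 / 33 per arm | 30% v 12%: difference | Power, 27 / 33 per arm |
|---|---|---|---|---|
| 0 | 30.0 | 66% / 75% | 18.0 | 40% / 45% |
| 5% | 29.5 | 64% / 73% | 17.5 | 37% / 43% |
| 10% | 29.0 | 63% / 72% | 16.9 | 36% / 42% |
| 20% | 27.8 | 59% / 68% | 15.7 | 33% / 38% |
| 40% | 24.5 | 51% / 59% | 12.9 | 26% / 31% |

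At 50% v 20% with 27 per arm, the expected number voided runs from 27 × 0.5 × 0.05 = 0.7 to 27 × 0.5 × 0.40 = 5.4 on placebo, and from 0.3 to 2.2 on drug.

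A weaker assumed effect gives the same direction. With 50% v 25%, a normal approximation and 26.7 per arm, the 25.0-point difference reads 24.3, 23.4 and 20.8 at e = 10%, 20% and 40%. Power falls from 47% to 44%, 42% and 35%.

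**No drug effect.** Equal e gives no false difference. When e differs by arm:

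| e, one arm v other | False difference, AMS 50% | Type I error, 27 / 33 per arm | False difference, AMS 30% | Type I error, 27 / 33 per arm |
|---|---|---|---|---|
| 10% v 10% | 0 | 5.2% / 5.2% | 0 | 5.3% / 5.2% |
| 10% v 5% | 1.3 | 5.2% / 5.4% | 1.1 | 5.4% / 5.3% |
| 20% v 10% | 2.9 | 5.8% / 5.8% | 2.3 | 5.7% / 5.7% |
| 40% v 10% | 9.9 | 10.8% / 11.9% | 7.4 | 9.4% / 10.2% |

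The 10% v 10% row is the reference, so that the discreteness of the test is not counted as bias.

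**Voiding unrelated to AMS.** Losing 10% of subjects at random gives no bias. At 50% v 20%, power falls from 65.7% to 61.3% (27 per arm) or from 75.4% to 69.8% (33 per arm).

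**The case against.** The strongest reply is that this is a deterrent, not an analysis rule. It sits among housing and meal arrangements, Compensation restates the sanctions without touching data, section F keeps de-identified data with no exception for violators, and section B treats baseline data as useful on their own. That does not rescue the wording. The sentence calls the data invalid for the whole study and derives expulsion from that, and silence elsewhere supplies no other meaning.

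Several other points do stand, in whole or in part:

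- **The bias mechanism is an inference.** No passage reports self-medication. Excluding people with migraine, keeping AMS short-lived and withholding pay may all limit it. Arm-dependent rulings are not shown, only not prevented.
- **The effect is small at low rates.** Voiding 5–10% of AMS cases moves a 30-point difference by at most 1 point. Clear type I inflation appears only in the extreme 40% v 10% case.
- **Contaminated samples matter for biomarkers.** Leaving out ferritin, hepcidin or C-reactive protein values after a subject takes iron or an anti-inflammatory product is reasonable. It does not justify voiding earlier measurements, and expulsion leaves few later samples.
- **Part of this is a wider gap.** The plan lacks analysis sets and missing-data rules for every outcome. An all-randomised rule would also reach withdrawals for COVID or pregnancy, and the sponsor should say so.

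**Conclusion.** The concern holds and should be fixed. The wording defect is firm: as written, the plan voids all data of randomised subjects for behaviour after assignment, and no analysis set corrects this. The loss of data collected before a breach follows directly.

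Bias in AMS is possible but not shown. It vanishes if violations are unrelated to outcome, or if the drugs have no effect and AMS cases are voided equally in all arms. Its size and direction depend on violation rates that the documents do not give. Over the assumed range it goes from negligible (about 1 point or less at 5–10% voiding) to material (5.5 points lost from a 30-point difference at 40% voiding, or a false 9.9 points at 40% v 10%).

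The trigger is also unclear. The policies in question follow the caffeine sentence as well as the ban, so a caffeine breach probably counts too. Yet the limit is two cups here, two six-ounce cups in the exclusion criteria and two 8 oz cups in the reminders in section E. Read literally, the drug ban also conflicts with staff-approved medication (inclusion table), permitted contraceptive use (Day 1) and treatment of severe altitude illness (section G).

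**What to change.** 1. Keep expulsion and prorated payment as conduct rules; Compensation already states both. Delete the clause that voids the data.
2. Add an analysis-set sentence: *All data collected from every randomised subject are analysed in the assigned arm.* State that it covers other withdrawals too, if that is intended.
3. Log each violation as a protocol deviation with four fields: substance, date, reason, and whether the person who ruled on it knew the arm.
4. Report the analysis without violators only as a sensitivity analysis, including for the iron and inflammation biomarkers listed under Blood measures.
5. State how outcomes missing after removal are handled. The choice of method is the sponsor's.
6. Say whether the caffeine limit is one of the policies meant, and reconcile the passages on caffeine, permitted medication, contraceptives and treatment of severe altitude illness.

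The cost is one deleted clause, two added sentences, four log fields, one sensitivity analysis and the reconciled wording, with no new visits. The downside is that some contamination stays in the main analysis, chiefly of biomarkers, which the sensitivity analysis addresses. Outcomes after removal remain missing.

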Overview: The initial components of the study will be performed over 6 days at baseline to 1) screen subjects for inclusion in the study and 2) obtain baseline measurements, with all studies conducted at the Cardiopulmonary Lab, Eugene, OR. These screening and baseline studies will be followed by 4 weeks of placebo or drug interventions (Cardiopulmonary Lab, Eugene, OR) and 14 days living at high altitude (Breckenridge or Leadville, CO). Within 1 week after returning to Eugene, OR, post-altitude measures will be made. Refer to Figure 1 below for a schematic representation of the timing and location of measurements. Each subject, regardless of intervention arm, will perform all protocols described below. All screening in Eugene, OR is scheduled for 6 days, but screening could take up to 10 days in the case of equipment malfunction or if the subject prefers to spread tests out over additional days.

* Indicates protocol that will be done on either day listed in early or mid altitude measures

What follows is a detailed description of each study day:

BASELINE: EUGENE, OR RESEARCH SITE

All studies done in Eugene will be done in either laboratory space within Pacific Hall and/or on running tracks and trails within the Eugene/Springfield metropolitan area or very close to this community.

Any subject with childbearing potential will be required to take a pregnancy test on VO₂max days and Hemoglobin mass testing days (both at baseline and altitude) as the other testing days will not involve any activity that would otherwise affect the fetus.

Day 1 – Informed consent, medical History, blood draw: Cardiopulmonary Lab, Eugene, OR (~60 min)

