Subjects will complete the Lake Louise Questionnaire (LLQ) and Environmental Symptoms Questionnaire (ESQ) to determine acute mountain sickness (AMS). Subjects will be instrumented with a pulse oximeter to measure oxygen saturation (~15 minutes).

Lastly, subjects will have resting ventilation and HCVR measured (~15 minutes).

Day 4 – VO₂max testing day: Cardiopulmonary Lab, Eugene, OR (~30 min)

Subjects will perform a VO₂max test (~30 minutes). Additionally, resting, exercise, and post-exercise heart rate and systemic blood pressure will be measured. Any subject with child bearing potential will be required to take a pregnancy test prior to the VO₂max test.

All subjects will arrive at the Cardiopulmonary lab and will be given a telemetric core temperature pill to take 5-10 hours before arriving for **Day 5** testing. If subjects do not take the pill the night prior to exercise testing, they will have to take the temperature pill as a suppository the morning of testing.

To take the core temperature pills, subjects will be told to swallow with a glass of water or other beverage. There are no restrictions for fluid or food consumption after the pill has been ingested and subjects will be told not to chew the telemetric pill. In order to insert the pill as a suppository, subjects will be instructed to insert the pill past the first digit of your finger and given lubricant and a glove to assist with the insertion process. Research staff will be available to give additional information about the insertion process if subjects have more questions. These directions apply to every time subjects take the core temperature pills.

Day 5 – Performance Stabilization, Eugene, OR (occurs ~30 days before departure for Colorado) (~30 min)

To further ensure accurate baseline measurements of physical performance, the top 80 subjects (and 20 alternates) with the most similar physical characteristics will repeat the 5K. This strategy will minimize the influence of learning effects associated with the tests and facilitate matching between groups. (~30 min).

Day 6 – Hemoglobin mass, Eugene, OR (occurs ~30 days before departure for Colorado) (~75 min)

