Within 1 week of returning to Eugene, OR, subjects will return to the Cardiopulmonary Lab (Eugene, OR) to repeat the 5k run and blood draw only. Tests will be performed over post-Altitude days 3-5. The 5k run will be done either on the same day as the other tests, or on a separate day depending on subject availability. Total blood draw 60 mL.

Note: During the 14 days at high altitude, subjects will be involved in data collection on days 1, 2, 3, 7, 8, 13 and 14. On all other days, there will be group activities and the possibility for subjects to hike or bike ride in small groups. They will not participate in any research activities during these “off” days, and they will be reminded frequently to follow CDC guidelines for COVID-19 risk mitigation (see ‘COVID-19 exposure scenario’ below).

Description of Data Collection Procedures:

Pulmonary Function Tests: Subjects will perform standard non-invasive spirometry to measure a maximal inspiratory and expiratory flow-volume loop, forced vital capacity (FVC), slow vital capacity (SVC), forced expiratory volume in 1 sec (FEV1), and mid expiratory flow (FEF25-75%). These tests will require the subject to blow in and out of a mouthpiece connected to a computerized flowmeter (pneumotachometer). This is a routine clinical test.

VO_{2max} tests: The VO_{2max} test will be an incremental test to volitional exhaustion on a cycle ergometer. Subjects will breathe through a mouthpiece and will begin cycling at a low resistance (50 W), with the resistance increasing every minute by 25 W. The test will continue until the subject reaches volitional exhaustion or a plateau in VO₂ as measured by our metabolic cart (Medgraphics Ultima CPX) is reached. During the entire protocol, subjects will breathe room air through a 2-way non-rebreathing small sampling flowmeter (pneumotachometer), which will allow us to measure

ventilation (V_E), VO_2 , and breath-by-breath metabolic data. Subjects will be instrumented with a forehead oxygen sensor to measure heart rate and SpO₂ at rest and during exercise.

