Before all tests, the subject will be telephoned or e-mailed (depending on preference) or told in person (while in Colorado) to confirm participation, remind them of the activities that will take place, checking for questions, and confirming continued interest and as a reminder to: 1) stay hydrated by drinking at least 2 liters of water a day, and 500 ml the morning of the test day; 2) to limit caffeine intake to the equivalent of two 8 oz cups of coffee a day; 3) limit exercise to that prescribed in the study design; with no exercise the day before the VO2Max, APFT and 5K tests; and 4) for exercise tests to time their eating so 1-2 hrs elapse between last meal and heavy exercise (VO2Max, 5K run or ruck hike). In addition, subjects will be emailed (while in Oregon) or reminded in person (while in Colorado) to complete their COVID-19 compliance survey prior to arriving to the lab.

A copy of the consent will be posted after the trial is closed to recruitment and no later than 60 days after the last visit by any subject in this study.

F. Provisions for Participant Privacy and Data Confidentiality

Each subject folder will be stored in locking file cabinets inside the primary investigators' locking offices ([name], [name], [name], or [name]). All other computer files associated with the subject will be identified only through their unique subject ID and stored on password protected lab computers. The de-identified data will be kept for at least 7 years after publication, per NIH guidelines. In the unlikely event the data are not published, they will be kept for at least 10 years after collection. This will ensure sufficient time for publication after data have been collected considering some trainees take up to 6 years to graduate, and often publication does not occur until many years after graduation.

Each subject will be assigned an ID using a random number code system consisting of three to five letters describing the study (e.g., COAST) and a random, non-repeating number (1-1000). This ID will be associated with their data folder, which will contain all study documents and data collected including all associated forms (i.e. informed consent document).

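### The rule against exercise on the eve of a 5k is left unprotected by the 6-day baseline schedule and by optional hiking or biking on altitude days 6 and 12

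*Combined protocol and SAP*

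**What the plan says.** **The rule.** Section E (Informed Consent Process) lists reminders given before every test. One is to "limit exercise to that prescribed in the study design; with no exercise the day before the VO2Max, APFT and 5K tests". Subjects are contacted by telephone or e-mail, "or told in person (while in Colorado) to confirm participation".

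**Baseline calendar.** The Overview in section C states that "The initial components of the study will be performed over 6 days at baseline". It adds that "All screening in Eugene, OR is scheduled for 6 days, but screening could take up to 10 days"; the stated reasons for the longer span are equipment failure or the subject's own preference. Day 4 is the VO2max test, described under data collection procedures as an "incremental test to volitional exhaustion on a cycle ergometer". On Day 5, "the top 80 subjects (and 20 alternates) with the most similar physical characteristics will repeat the 5K". The Day 5 heading also places that visit about 30 days before departure. The Day 4 entry covers the temperature pill for Day 5, with a fallback that begins "If subjects do not take the pill the night prior to exercise testing".

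**Altitude calendar.** The 5k is run on days 1, 7 and 13. The note at the end of the post-altitude section names days 1, 2, 3, 7, 8, 13 and 14 as data-collection days, then says: "On all other days, there will be group activities and the possibility for subjects to hike or bike ride in small groups".

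**Use of the 5k.** Aim 1 concerns exercise performance in the first 3 days, on days 7-8 and on days 13-14.

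**The concern.** The 5k is a timed all-out effort, repeated at baseline, three times at altitude and once afterwards. The plan recognises that prior-day exercise matters, because it forbids it. Yet the schedule appears to place a maximal test on one eve and offers optional exercise on two others. Staff and subjects would then hold instructions that do not agree.

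At stake is the comparability of runs within a subject. If Day 5 is the reference and is run tired, the slowing at altitude looks smaller than it is. If some subjects hike on day 6 or day 12, the change from day 1 to days 7 and 13 mixes acclimatisation with prior-day load.

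**Working it through.** The documents give no performance figure that bears on this, so the check is of the calendar.

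**1. Off days at altitude.** Days 1 to 14 less {1, 2, 3, 7, 8, 13, 14} leaves {4, 5, 6, 9, 10, 11, 12}, that is 14 - 7 = 7 days. The eve of the day 7 run is day 6 and the eve of the day 13 run is day 12. Both are off days, and the note makes no exception for them.

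**2. Gap between baseline Days 4 and 5.** Six numbered days in six scheduled days leave 6 - 6 = 0 spare days, so Day 5 falls one day after Day 4. In the 10-day span there are 10 - 6 = 4 spare days, but nothing assigns one of them to this interval.

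**3. The day before each 5k.**

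| 5k run | Day before | Result |
|---|---|---|
| Baseline Day 2 (in the fitness test) | Consent, examination, blood draw | No conflict |
| Baseline Day 5 (stabilization) | VO2max test, if days are consecutive | Conditional conflict |
| Altitude day 1 | No exercise scheduled; about 8 hours of travel precede the run | No conflict |
| Altitude day 7 | Off day 6, hiking or biking offered | Unprotected |
| Altitude day 13 | Off day 12, hiking or biking offered | Unprotected |
| Post-altitude days 3-5 | Day 14 rucksack carry is not the day before | No scheduled conflict |

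Total: 1 conditional + 2 unprotected + 3 without conflict = 6.

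**4. Which baseline run is the reference.** The plan does not say. The 5k description places the baseline run within the fitness tests, which points to Day 2. The core temperature section pairs the stabilization run with altitude days 1, 7 and 13, and the Day 5 entry says the repeat is there to make the baseline more accurate. Both point to Day 5. The baseline conflict affects the altitude comparison only so far as Day 5 is used.

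**5. Which comparisons are exposed.** The baseline calendar and the off-day rules are the same in every arm. A shift shared by all arms alters change from baseline and change between altitude days, but largely cancels when drug is compared with placebo.

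**The case against.** **The baseline days may not be consecutive.** Day 5 is tied to the departure date and limited to 80 subjects and 20 alternates chosen for similarity. Up to 300 people are screened, and choosing the most similar needs results from many of them. Stabilization is also paid separately from screening. The numbered days may therefore be visit labels, and the pill instruction gives no interval between Days 4 and 5. This stands: a breach at baseline is not established. But the Overview counts all six days within a 6-day schedule, and neither reading guarantees a rest day.

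**The reminder governs.** Outings are only a possibility, and the in-person reminder is specific to tests, so it could be read as limiting the general permission. This also stands in part: the rule is left unprotected, not broken by design. Still, the plan does not say how long before a test the reminder is given, and the off-day note offers what the reminder forbids.

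**Stronger readings that the documents do not support.** A reader might infer that subjects with less acute mountain sickness would go out more, so that a drug effect on sickness would change prior-day load by arm. The section on altitude risks expects this sickness to be gone by day 3, well before days 6 and 12. A reader might also try to express the problem as a share of the slowing at altitude. The documents give neither the effect of prior-day exercise on a 5k nor the expected slowing, so any such figure would rest wholly on assumption.

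**Conclusion.** The inconsistency is real and modest. On a face-value reading of the 6-day schedule, a maximal test falls the day before the Day 5 5k; the other timing statements make a gap plausible without requiring it. At altitude, optional exercise is offered on the eves of two of the three 5k runs, against the plan's own reminder.

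Prior-day exercise may therefore differ between the runs compared within a subject. It is a risk, not a demonstrated difference in rest. For the baseline part it depends on Days 4 and 5 being consecutive and on Day 5 serving as the reference. For the altitude part it depends on subjects taking up the outings despite the reminder. No size can be taken from the documents.

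The randomised drug-versus-placebo contrast is largely protected, because the rules are common to all arms. That protection would weaken only if uptake of outings differed by arm, and the plan gives no reason to expect this. The daily exercise log would allow it to be looked at, though no analysis use of the log is stated. The point is worth correcting because it touches an Aim 1 outcome and the correction is nearly free.

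**What to change.** 1. In the section C Overview and the Day 4 and Day 5 entries, require at least one exercise-free day between the VO2max test and the Day 5 5k. State it as a scheduling rule, since the longer span is now allowed only for equipment failure or subject preference. The schedule becomes 6 + 1 = 7 days, inside the 10-day allowance. The pill can still be handed out on Day 4, because its timing is set relative to Day 5 testing.
2. In the note on off days, exclude hiking and biking on days 6 and 12, so that it agrees with the reminder in section E.

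No change is needed to the other off days (4, 5, 9, 10 and 11), none of which is the eve of a 5k.

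The cost is protocol wording, one more calendar day at baseline, and less free choice for subjects on two off days.
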